5. TRIAL PROCEDURES

5.1 Recruitment

5.1.1 Patient Identification

All adult lung transplant recipients remain under life-long follow up. This follow up is focused on maintaining the patient's overall wellbeing as well as carefully monitoring their lung allograft health. Alongside regular clinic visits, patients have direct access to their centres to be reviewed at short notice if they develop any new symptoms especially those suggesting their lung health may be affected, such as cough, sputum production, shortness of breath or chest infection. As a result, any fall in lung allograft function from baseline that suggests possible new onset CLAD or progression of previously diagnosed but stable CLAD is investigated promptly to identify and treat any non-CLAD causes. If no alternative cause is identified, or if the treatment of any non-CLAD causes fails to correct the fall in function, then all patients, who have not previously been treated with prolonged neomacrolide therapy, should receive a trial of azithromycin 250-500mg three times/week for at least 6 weeks. If the azithromycin, in this case given for anti-inflammatory rather than antibiotic properties, fails to show any effect and lung function continues to decline, then CLAD is confirmed and the patient may be eligible to participate in E-CLAD UK.

5.1.2 Pre-Screening for Study Participants: Recommendations

To ensure that all potentially eligible patients are approached in a timely manner, it is important that bilateral lung, or heart and bilateral lung transplantation patients with early and progressive CLAD are identified in pre-screening. This will enable a timely approach to potentially eligible participants. It is recommended that the following patients should be monitored in clinical practice as patients who may become potentially eligible:

1. Patients undergoing investigation for a new >10% fall in FEV1 where a potentially reversible is either not identified or is treated and response to treatment assessed.
2. Patients commencing a trial of long-term azithromycin therapy due to a drop in lung function
3. Patients with an FEV1 between 85-51% of personal best FEV1 value post-transplant (equivalent to New ISHLT CLAD Stages 1 and 2) with evidence of CLAD progression
4. Patients with an FEV1 >85% of personal best FEV1 associated with a ≥ 200 mL decrease in FEV1 in the previous 12 months.

These patients will not be formally approached at this time and no screening data will be collected on these patients; this is a recommendation for clinicians to pre-screen their caseload for future potential participants. These participants will only be formally screened and approached regarding potential participation in the trial once a new CLAD diagnosis, or progression of existing CLAD is suspected.

5.1.3 Screening

All patients aged 16 and over who have received a bilateral (single sequential) lung or heart and (bilateral) lung transplantation and completed a trial of azithromycin therapy for suspected CLAD will be screened for eligibility. Patients aged 16 and over with an existing diagnosis of CLAD who had previously stabilised but in whom lung function is declining due to potential progressive CLAD will also be screened for eligibility.

Patients who have previously responded to a course of azithromycin but went on to develop CLAD subsequently are still potentially eligible even if they are continuing longer term azithromycin for non-CLAD benefits.

An electronic screening log, integrated into the Sealed Envelope Redpill database will capture anonymised screening data including:

- The number of participants presenting with suspected CLAD and commenced/completed a course of azithromycin.
- Number of patients approached and provided with a PIS.
- The number of patients eligible/not eligible and reason (e.g. responded to azithromycin and CLAD excluded).
- Eligible patients approached for consent.
- Eligible patients not approached and the reasons why.
- Patients declined/not consented and the reasons why (if known).

5.1.4. Initial Approach

The initial approach to the patient regarding the trial will be by the treating clinician who will explain that they may be eligible to take part in a clinical trial. Potentially eligible patients will be provided with a short study participation information sheet (PIS) and an explanation of the purpose of the study and what it would involve. If having read this the participant is interested in receiving more information a copy of the full participation information sheet (PIS) will be provided. The patient will be advised to read the full information sheet carefully and discuss the trial with members of their family and/or GP if they feel this would be beneficial. The patients will be advised that they will be given the opportunity to ask any questions and discuss the trial and their eligibility in more detail at their next appointment. All patients will be given a minimum of 24 hours to consider participation to ensure they understand what the study involves and the risks for them.

5.1.5 Consent

When progressive CLAD is confirmed written informed consent must be obtained prior to any research assessments being carried out.

Formal written consent and confirmation of eligibility to participate in the trial will be taken by the site PI or delegated local Co-Investigator. The consent form will indicate consent to be approached to participate in the optional qualitative interview sub-study as well as the main study. Those who do not wish to take part in the qualitative sub-study will still be able to participate in the main trial.

Consent will also be sought for access to data generated during longer-term clinical follow up, this is also not mandatory for participation in the trial.

The original signed Consent Form will be filed in the Investigator Site File (ISF) and a copy filed in the patient clinical notes. Copies of the PIS used will also be filed in the ISF and clinical notes. Consent must be received prior to any trial specific assessments.

A copy of the completed consent form will also be sent by site to the secure NCTU email [contact] – this is for safety monitoring purposes. As this document contains patient identifiable information, an nhs.net account must be used to send this document. For sites that do not have nhs.net accounts, another secure method may be used but this must be discussed with and agreed by the NCTU Trial Manager(s) prior to use.

Confirmation of on-going consent to continue participating in the trial will be sought at the start of each follow-up visit and documented in the participant's medical notes.

Eligibility for the trial must be confirmed by a clinical member of the team who is delegated this task on the trial delegation log. An eligibility checklist must also be completed and signed by the member of the clinical team delegated to this task. The original eligibility checklist will be filed in the ISF and a copy will be filed in the participant's medical record. A copy of the completed eligibility checklist must also be sent by site to the secure NCTU email [contact] – again this is for safety monitoring purposes

5.2 Baseline Assessments & Data Collection

After written informed consent is obtained the baseline assessment and data collection will be carried out. See 5.6 for Schedule of Events.

5.2.1. Pregnancy test

Where indicated a urine dip stick test will be carried out at baseline only (see section 4.3). This should be carried out before any other baseline assessments and if positive the patient will be withdrawn from the trial, no further data will be collected and advice regarding pregnancy provided by the clinical team.

5.2.2 Safety blood tests

Safety bloods may identify a contraindication to ECP or values where the ECP treatment may require caution or modifications if the participant were to be randomised to the ECP arm.

- Urea and electrolytes
 - Caution in patients with low eGFR<30mL/min as will need to tolerate the fluid changes associated with ECP and will require closer monitoring.
 - Patients with end-stage renal disease who are dialysis dependent should not have haemodialysis performed on the same day as ECP treatment
- Liver Function Tests (LFTs)
 - High Bilirubin levels >3xUpper Limit of Normal may require adjustment of the Bowl optic sensor in the CELLEX ECP system
- Full Blood Count (FBC)
 - A total white cell count of >25 x10⁹ per litre **is a contraindication to ECP**
 - A haematocrit <27% will require a large extra-cellular volume draw during ECP treatment and may cause haemodynamic instability. Blood transfusion prior to treatment or a blood prime at the time of ECP treatment will be required. A risk assessment of enrolling a participant with HCT <27% should be made by the PI considering all other co-morbidities.
 - A platelet count <20.0 × 10⁹ per litre will require platelet transfusion and avoidance of heparin anticoagulation during ECP treatment.

If safety bloods indicate either a contraindication, caution or modification to ECP treatment, then the results and implications are to be discussed with the patient before deciding whether to continue in the study or not. The results of safety bloods must be shared by the research team with the ECP delivery team to ensure any additional requirements are implemented.

In the event that heparin is contraindicated during ECP treatment, then alternative suitable anticoagulants such as citrate may be used during the ECP process.

5.2.3 Routine Data Collection and Routine Clinical Assessment

The following routinely collected information and clinical assessments will be collected:

- Demographics:
 - Sex at birth.
 - Date of birth & current age.
 - Ethnicity.
- Relevant past medical history (PMH) and current treatment:
 - Details of history of disease.
 - Relevant PMH.
 - Current medical conditions (recorded to month/year of onset where possible).
 - Surgical interventions (previous and planned).
 - Any non-drug therapies.
- ISHLT CLAD stage and CLAD phenotype (definitions in section 7)
- Results of routine clinical assessments:
 - Most recent chest X-ray.
 - Most recent PFT Spirometry FEV1/FVC and values from the preceding 12 weeks (minimum 2 readings obtained at least 3 weeks apart and at least 3 weeks prior to consent plus the baseline recordings)*.
 - Physical examination assessments.

* In the event that there are not at least 2 readings including the study baseline within the 12 week period preceding the baseline visit, then data can be collected up to 26 weeks prior to baseline visit. These will ideally have been collected at clinical appointments but home readings are acceptable.

5.2.4 Research Specific Assessment

The following research assessments will be carried out at baseline;

- Full Pulmonary Function Tests (PFT):
 - Spirometry comprising FEV1 and FVC.
 - Flow Volume Loop including FEF25-75
 - Static Lung volumes comprising Total Lung Capacity (TLC) and Residual Volume (RV).
 - Total diffusing capacity (DLCO), alveolar volume (Va) and volume corrected diffusing capacity (KCO).
 - Pulse oximetry at rest.
- Research blood samples
 - 1 x 6ml lithium heparin tube
 - 2 x 4ml serum tubes
 - 1 x 3ml RNA tube

(see section 5.4.4 and E-CLAD UK laboratory manual for processing and storage information)

- 6MWT

- To prevent any delays in initiating ECP (should the participant be randomised to that arm) assess suitability of venous access at baseline visit and determine if peripheral cannulation is possible or whether a central venous catheter may be required

5.2.5 Patient Reported Outcome Measures

- EQ-5D-5L questionnaire.
- SF-36 v2 questionnaire.

5.3 Randomisation

Following completion of baseline data collection, participants confirmed as eligible for the trial will be randomised by a delegated and trained member of the research team.

5.3.1 Randomisation details

Participants will be randomised to receive either ECP plus SOC (treatment arm) for 24 weeks or SOC (control arm) alone. Two variables will be used to achieve a balanced allocation of participants between the two trial arms:

- Site
- CLAD phenotype – RAS / BOS / mixed (For definitions see section 7)

Stratified block randomisation, targeting 1:1 allocation to the two trial arms, will be used. The trial is not blinded and so no arrangements will be required for unblinding.

5.3.2 Randomisation System

Randomisation will be carried out by a delegated and trained member of the research team at each site using Sealed Envelope's randomisation system which is, a central, secure, 24-hour web-based randomisation system integrated into the Red Pill database.

Randomisation system web address:

<https://www.sealedenvelope.com/access/>

The system is available 24 hours a day, 7 days a week

This should be done during the patient's baseline visit in order to simplify arrangement of an initial ECP visit if patient randomised into this arm.

In the event that the online randomisation system is not accessible, the site team should contact the NCTU data management team within normal working hours (9am – 5pm Monday to Friday, excluding bank holidays and Newcastle University closures):

E-mail: [contact]

5.3.3 Blinding

This trial is unblinded. Study participants, clinicians and the NCTU team will be aware of treatment allocation. The Statistical Analysis Plan (SAP) will be developed by statisticians who are unaware of

treatment allocation and will be finalised and signed-off prior to unblinded data being reviewed by the DMC. The SAP will contain full details of the final analyses, with details of who will perform these analyses. Trial statisticians will have access to unblinded data for the purposes of creating DMC reports. No other members of the research team will have access to the unblinded data contained in closed DMC reports, unless the DMC request that unblinded information is released. In the case that a major amendment is proposed to the SAP, this will be approved by an appropriate blinded independent statistician (the independent Trial Steering Committee statistician or an appropriate senior member of the Biostatistics Research Group).

5.4 Follow up assessments and Data Collection

5.4.1 Schedule of Events

Activity	Screening at clinical assessments	Week 0**		Week 2 +/- 7 days	Week 4 +/- 7 days	Week 6 +/- 7 days	Week 8 +/- 7 days	Week 10 +/- 7 days	Week 12 +/- 7 days	Week 16 +/- 7 days	Week 20 +/- 7 days	Week 24 +/- 7 days ****
		Baseline Visit	ECP only* (0-14 days)	ECP only	Research Assessment	ECP only	Research Assessment	ECP only	Research Assessment	Research Assessment	Research Assessment	Research Assessment
Screening												
Screen medical notes	x											
Provide PIS	x											
Initial Eligibility check	x											
Consent												
Informed Consent		x										
Confirmation of eligibility		x										
Pregnancy Test		x										
Randomisation		x										
Safety Bloods (FBC, U&E, LFT)		x										
Routine Data Collection												
Demographics		x										
PMH		x										
Clinical/physical assessment		x			x		X		x	x	x	x
Routine blood tests***					x		X		x	x	x	x
Chest X-ray findings		x			x		X		x	x	x	x
Medication review		x			x		X		x	x	x	x
PFT Spirometry (FEV/FVC)		x			x		x		x	x	x	x
Survival status												x
Research assessments												
Research Bloods		x							x			x
6 MWT		x										x
EQ-5D-5L		x										x
SF-36 v2		x										x
ISHLT CLAD score		x										x
Research full PFT		x										x
AE & SAE Reporting			x	x	x	x	x	x	x	x	x	x
Assessment of Response									X*****			
Assess if cannula possible or catheter required		x										
ECP arm only												
ECP Cycle (2 days) + clinical bloods			1	2	3	4	5	6	7	8	9	
∞Pre and post ECP (NCL only) (2 x 20mls)			x						x		x	
*The first ECP cycle should ideally take place within 14 days of randomisation. If ECP cycle 1 is >28 days after randomisation this should be documented as a deviation If ECP cycle 1 is >14 days after randomisation then baseline Spirometry should be repeated ****Visit window extended to +30 days if participant believed to have treatable non-CLAD condition at time of planned visit					**Follow up assessments are from date of randomisation in control arm, and from date of commencing ECP for intervention arm. *** Routine Blood Tests – Full Blood Count, Urea and Electrolytes and Liver Function tests ***** For those in the ECP arm participants must have received 6 treatment cycles prior to the formal 12 week assessment of response taking place – see sections 5.4.5 and 5.5.1 for details ∞ Pre and Post ECP research Blood for apoptosis assay in Newcastle participants only for mechanistic sub study							

5.4.2 Follow up Assessment time points for all participants

Follow up assessments will take place at 4, 8, 12, 16, 20 and 24 weeks (see Schedule of Events in section 5.4.1). For participants in the SOC arm week 0 will be baseline assessment. For participants in the ECP arm week 0 will be from the day the first ECP treatment is commenced. At the 12-week assessment all participants will be reviewed to identify non-responders in both groups (see section 5.5).

Follow up visits should align with routine clinical appointments where possible. Visit windows have been incorporated into the schedule of events (see section 5.4.1) to enable assessments and collection of routine data in line with the regular clinical visits already attended.

5.4.3 Routine Data Collection for all participants

The following routinely collected information will be collected **at each assessment** time point (4, 8, 12, 16, 20 and 24 weeks):

- Changes to CLAD related symptoms.
- Changes to medication or non-drug therapy.
- Changes to routine clinical care.
- Any changes in treatment or new surgical interventions.
- Change in ISHLT CLAD stage.
- Additional clinic visits, urgent and unscheduled clinical assessments, or hospital admissions since previous assessment

The following routine clinical assessment results will be collected (preferably day of assessment):

- Most recent routine bloods (FBC, U&E's, LFT's).
- Most recent chest X-ray.
- Most recent PFT spirometry FEV1/FVC.
- Physical assessments.

5.4.4 Research Blood Samples for all participants

The following research bloods samples, will be taken from all participants at study baseline, 12 and 24 weeks for mechanistic analysis and evaluation of immune response

- 1 x 6ml lithium heparin tube
- 2 x 4ml serum tubes
- 1 x 3ml RNA tube

Processing of blood samples at site

- 1 x 6ml lithium heparin tube
 - This sample will be used for immunophenotyping. Immediately after collection the blood tube should be mixed well by inverting 8-10 times.
 - Sample can be kept at room temperature prior to shipping
 - Sample should be shipped on the day of collection (see E-CLAD UK laboratory manual for details)
- 2 x 4ml serum tubes
 - These samples will be used for immune marker analysis
 - Samples should be left at room temperature for 30-60 mins before processing

- Processed samples should be stored in -80°C freezer then batch shipped (see E-CLAD UK laboratory manual for details)
- Any sample remaining after the separation of serum should be disposed of in accordance with local policy.
- 1 x 3ml RNA tube
 - This sample will be used for transcriptomics
 - After collection, the blood tube should be mixed well by shaking or briefly vortexing contents
 - Samples should be stored in -80°C freezer then batch shipped (see E-CLAD UK laboratory manual for details)

The research blood samples will be analysed by a central laboratory at either Newcastle University or a commercial laboratory called Melio Health.

The samples going to Melio Health (those in the lithium heparin tubes) must be received by them the day following collection (ideally within 24 hours of collection). As Melio Health is only able to accept samples Monday-Friday, this means that these samples will need to be collected Monday to Thursday. Royal Mail safe boxes will be used to send these samples using overnight next day delivery. Sites must ensure that they know what time the last post collection is from their hospital post room and ensure samples are at the post room in time for the last post. This may mean that a morning appointment for the baseline, 12 week and 24 week visit will be necessary.

For participants receiving ECP, these bloods should be taken prior to commencing the treatment cycle that coincides with the visit where research bloods are due. There should be a minimum of 10 days between the previous cycle of ECP finishing and the 12 week research bloods being collected.

The week 12 research blood sample is to be collected even if the patient is classed as a non-responder following the 12 week assessment of response.

For full details about how all bloods must be collected, processed, labelled and packaged, see the blood sample section of the E-CLAD-UK laboratory manual.

5.4.5 12 Week Assessment of Response

All participants will be reviewed at 12 weeks to assess response and identify non-responders in both groups. Response will be determined by the % change in the FEV1 or FVC compared to baseline measurements obtained from routinely collected PFT Spirometry data (see 5.5 for identification of non-responders).

It is important to distinguish if a decline in FEV1 or FVC is due to progressive CLAD or potentially a non CLAD cause (see section 5.5).

For participants allocated to ECP treatment, the 12 week assessment of response must be completed and the decision made to continue treatment before a participant receives their 7th cycle of ECP treatment. This assessment should take place on the same day as the scheduled ECP treatment or as close to as possible.

If a participant receiving ECP is identified as a non-responder due to progressive CLAD, ECP may be continued if it is felt by the PI to be of clinical benefit, whilst alternative rescue therapies are being arranged if appropriate. See section 5.5.1 for additional details.

Please note: for participants in the ECP arm, 6 treatment cycles must have been received prior to the 12 week assessment of response taking place (see section 5.5.1). This may mean the 12 week assessment of response taking place later than 12 weeks if previous ECP treatments have been delivered towards the end of the visit windows outlined in the schedule of events. If the assessment still takes place within the protocol window (i.e. 12 weeks +/- 7 days) this is fine, if the assessment takes place outside of this window (i.e. from weeks 13 onwards) this would need to be recorded on the site deviation log.

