2. OBJECTIVES AND OUTCOME MEASURES

2.1 Primary Objective

To determine if ECP therapy plus SOC is more effective at stabilising lung function in lung transplant recipients with CLAD compared to SOC alone.

Lung function stabilisation will be derived from change in FEV1 and FVC at 12 and 24 weeks compared to baseline at study entry. The primary outcome measure is a composite responder outcome, which is defined as both 'lung function stabilisation' from baseline to 24 weeks and 'no rapid decline' as measured from baseline to 12 weeks (see section 7 for definitions).

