3.3 Flow Charts of Study Design and Research Activity

3.3.1 Overview of Study Design

3.3.2 Flow Chart of Research Activity

3.4 Primary and secondary outcome measures/endpoints

3.4.1 Primary outcome measure

Lung function stabilisation will be derived from change in FEV1 and FVC at 12 and 24 weeks compared to baseline at study entry. At baseline and 24 weeks FEV1 and FVC will be taken from Full Pulmonary Function Tests (PFT) carried out as a research assessment. At 12 weeks FEV1 and FVC values will be taken from those collected as part of routine clinical assessment.

Full Pulmonary Function Tests

Full pulmonary function tests to include FEV1, FVC, FEF25-75, Flow-volume loop, TLC, RV, Va, TLCO and KCO should be performed in a fully accredited lung function laboratory by or under the close supervision of a qualified pulmonary physiologist. Results should be provided as absolute values, % predicted values and z-scores. All spirometry should be performed according to ATS/ERS standards. If a bronchodilator response is performed, then post-bronchodilator FEV1 and FVC values should be reported.

Routine spirometry tests

Routine clinic spirometry as collected regularly in the transplant clinic should be performed in accordance with usual clinical practice in the transplant centre by a trained individual able to ensure adequate reproducibility/quality control of the test and reporting of absolute values of FEV1 and FVC. Tests can be performed in either an accredited lung function laboratory or using a desktop or handheld spirometer as long as adequately supervised. Interpretation of the routine spirometry will be by the participant's lung transplant physician. Home spirometry results performed by participants using a handheld spirometer already in their possession can be used in place of routine clinic spirometry if it is not possible for the participant to attend. In such cases the principal investigator must be confident the participant is trained in its use and able to perform reproducible spirometry. Home spirometry cannot be used to replace the baseline and end of study full pulmonary function tests or the 12-week assessment time point.

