5.7 Additional information and data collection at ECP visits

Participants allocated to receive ECP will attend their respective ECP unit for treatment at 0, 2, 4, 6, 8, 10, 12, 16, 20 weeks. At weeks 4, 8, 12, 16, 20 and 24, data regarding the patient's condition, lung function and changes to CLAD treatment will also be collected and recorded in the eCRF. Where the ECP treatment visit aligns with the follow up assessments (4, 8, 12, and 20 weeks), the research assessments should take place prior to the ECP treatment commencing.

Ideally sites should try to adhere to 14 days between ECP treatment cycles wherever possible. For cycles 1-7 and 28 days for cycles 8 and 9. Where this is not possible there should be a minimum of 10 days between ECP treatment cycles. and a maximum of 21 days between ECP treatment cycles.

The clinical assessments and blood samples taken at the ECP treatment visits are for clinical purposes to ensure it is safe to proceed with treatment and should take place prior to commencing the ECP treatment cycle as per usual clinical practice, matching those normally performed at each ECP unit. Any results necessitating alterations to the standard ECP protocol or deferment of treatment are to be recorded in the eCRF. There are no additional research assessments to be undertaken at each ECP treatment visit.

AE and SAE reporting and concomitant medication review should coincide with each trial visit. For weeks 2, 6 and 10 where patients receive ECP treatment but are not required for routine clinical assessment, details may be collected by the research team via a telephone call to the patient. For information on reporting AEs and SAEs, including those identified during the ECP procedure see section 8.2.

All participants in the ECP arm must be followed up for a minimum of 4 weeks after the last ECP treatment and any adverse events noted during this time reported as per section 9.

A data card comes as standard with each ECP treatment kit. This is inserted into the machine and collects data about the machine settings and the way the treatment went. For participants in the E-CLAD UK trial we are asking ECP teams to follow the steps below:

1. Record the ID of the ECP treatment kit on the participants treatment record – this links the participant to the kit that was used to treat them and the card that will contain the treatment data.

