5.8 Data collection if patient unable to attend visits

There may be situations where a patient is unable to attend for study visits, for example due to needing to isolate because of COVID-19. Wherever possible, this should be rearranged to another time within the visit window (please see section 5.4.1 Schedule of Events for details regarding visit windows). If this is not possible then the visit should be arranged to take place remotely with as many procedures completed as possible. This should include spirometry where the patient has access to suitable equipment at home and is required for a study visit. Home recorded FEV1 and FVC values should not be used as definitive readings for classifying non-responders.

The week 12 assessment of response visit must take place in clinic and cannot be completed remotely. If a patient is unable to attend a planned week 12 visit then it should be rearranged to another time within the visit window. If this is not possible then it should take place as soon as possible outside the window and reported as a deviation.

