7.3 Lung Function

Lung function stabilisation – defined as a less than or equal to a 10% loss in FEV1 and FVC from study baseline to 24 weeks.

Rapid decline – defined as a greater than 20% fall in FEV1 or FVC in the first 12 weeks from study baseline.

Non-responders – As outlined in the study flow chart in Section 3.3, a non-responder is defined as someone who experiences a decline in FEV1 or FVC of more than 10% at 24 weeks compared to baseline readings due to progressive CLAD. A non-responder may also be someone with a decline in FEV1 or FVC of >20% within 12 weeks of the baseline visit that is confirmed as being due to progressive CLAD.

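### In the ECP arm only, the formal week-12 response assessment waits for six cycles with no latest date, although rapid decline is defined by calendar time from baseline

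*Protocol*

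**What the plan says.** - **Endpoint definition.** Section 2.1 requires both stabilisation at 24 weeks and no rapid decline, the latter "as measured from baseline to 12 weeks". Section 7.3 gives rapid decline as "defined as a greater than 20% fall in FEV1 or FVC in the first 12 weeks from study baseline". Both are calendar definitions and apply to both arms.
- **Source of the reading.** Section 3.4.1: "At 12 weeks FEV1 and FVC values will be taken from those collected as part of routine clinical assessment".
- **Condition on the assessment, ECP arm only.** Section 5.4.5: "for participants in the ECP arm, 6 treatment cycles must have been received prior to the 12 week assessment of response taking place". The 5.4.1 footnote: "For those in the ECP arm participants must have received 6 treatment cycles prior to the formal 12 week assessment of response taking place". Section 5.5.2, on the SOC arm, has no counterpart.
- **Delay foreseen.** Section 5.4.5: "This may mean the 12 week assessment of response taking place later than 12 weeks". An assessment outside +/- 7 days goes on the deviation log. For a missed week-12 visit, 5.8 says "it should take place as soon as possible outside the window and reported as a deviation". Neither section gives a latest date.
- **Cycle spacing.** Section 5.7 aims for 14 days between the early cycles, with a minimum of 10 days "and a maximum of 21 days between ECP treatment cycles". The 5.4.1 schedule gives each cycle after the first its own +/- 7 day window.
- **Use of the result.** Non-responders count as not stabilised and may leave for rescue treatment (5.5.3). The week-12 change enters the joint model, and a fall of more than 20% at 12 weeks defines a sensitivity analysis (10.3.1).

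**The concern.** A component of the primary endpoint is defined by time since baseline, but in one arm its formal assessment is triggered by the amount of treatment received. Two things follow. An ECP participant whose cycles slip may be read later than any SOC participant. One who stops ECP early for access failure, infection or choice, and keeps attending as 5.11 encourages, never meets the stated condition.

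The comparison is by intention to treat (10.2), so when and whether an outcome is read should not depend on exposure to the allocated treatment. At stake are the week-12 mean in the joint model, the rapid-decline classification, and, through rescue and withdrawal, who has week-24 data. The point is separate from the two arms' different week-0 definitions and would remain if those were aligned.

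**Working it through.** Days are counted from each arm's own week 0 (5.4.2): the baseline assessment in SOC, the first ECP day in the ECP arm.

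**1. The week-12 window.** 12 x 7 = 84, so +/- 7 days gives days 77 to 91. Section 5.4.5 describes out-of-window assessments as those from week 13 onwards; 13 x 7 = 91 agrees.

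**2. Cycles given within their windows.** Cycle 6 is due at week 10 +/- 7 days, so at the latest on day 10 x 7 + 7 = 77. Cycle 7 after the 10-day minimum is day 77 + 10 = 87; after the preferred 14 days it is day 77 + 14 = 91. Both are inside the window, so on-schedule treatment does not force a late assessment.

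**3. Cycles behind their windows.** Take two gaps of 21 days and three of 14, each allowed by 5.7. Cycle 6 falls on day 2 x 21 + 3 x 14 = 84, which is 84 - 77 = 7 days past its 5.4.1 window. Sections 5.7 and 5.4.1 therefore disagree on whether this sequence is on schedule. Cycle 7 is then at day 84 + 10 = 94 or later, at least 3 days past day 91. Section 5.4.5 prefers the assessment on the day of the scheduled treatment, so this one would be late. It could still be made by day 91 if uncoupled from cycle 7, because six cycles would have been received. Further slippage removes that option.

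**4. Fewer than six cycles.** Side by side:
- 5.4.1 and 5.4.5: six cycles must precede the formal assessment.
- 5.4.2, 5.5 and the opening of 5.4.5: all participants are assessed at 12 weeks.
- 5.11: those stopping for reasons other than progression are encouraged to continue visits and assessments.

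No sentence exempts the early stopper from the first rule. The protocol does not give the share affected. If it were 5% to 20% of the 45 per arm (an assumption), that is 0.05 x 45 = 2.25 to 0.20 x 45 = 9, or about 2 to 9 participants.

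**5. Effect on the composite.** A responder needs no rapid decline and at most 10% loss of FEV1 and FVC at week 24. Anyone with more than 10% loss at week 24 fails whatever the week-12 reading. Where a week-24 value exists, the timing of the week-12 reading therefore matters only for participants who end within 10%:
- A participant who first passes 20% after week 12, is read late, then recovers to within 10% is wrongly failed. This counts against ECP.
- A participant above 20% at week 12, not formally read then, improved by the late reading and within 10% at week 24 is wrongly passed. This counts for ECP.

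Both paths need a substantial recovery, so they should be uncommon. A steady decliner who passes 20% at any earlier date is still beyond 20% at week 24. Where the week-24 value is missing because the participant left for rescue, the classification itself carries the outcome, and its timing matters more.

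**The case against.** The strongest defence is that the protocol already supplies most of what is needed. The schedule lists spirometry and assessment of response as separate rows, and the six-cycle footnote attaches to the formal assessment only. Week-12 spirometry is scheduled for everyone, and 3.4.1 takes the endpoint values from routine spirometry. A fall of more than 20% before week 12 is acted on (5.5), and the investigator may declare non-response before six cycles (5.5.1). The protocol gives a reason for six cycles, namely enough exposure to judge the treatment. Which reading enters the model could be settled in the SAP, which is not at hand. All of this stands and limits the size of the problem. It does not remove the conflict between a calendar definition and an exposure condition within the protocol itself.

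Three stronger readings are tempting but not supported:

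- **Assessment at week 15 or 16 changes the primary outcome.** Gaps of 21 days throughout give cycle 6 on day 5 x 21 = 105 (week 15) and cycle 7 from day 115 (week 16.4). But cycle 3 would then fall on day 42 against its limit of day 35, so this needs repeated off-schedule cycles. A reader might add the pre-ECP decline of 116 mL/month quoted in 1.2 and an assumed baseline of 1.7 L: 0.116 x (12/4.345)/1.7 = 18.8% at week 12 and 23.6% at week 15. The same participant has lost 37.7% by week 24 and fails whenever read. At 28.9 mL/month the loss is 9.4% by week 24 and never approaches 20%. The crossing also depends on the assumed baseline: at 1.5 L the fall is already 21.4% at week 12, and at 2.1 L it is still 19.1% at week 15.
- **Early stoppers are never measured.** The text supports only the absence of a formal assessment; their spirometry remains scheduled.
- **Early stoppers drop out of the analysis, favouring ECP.** Section 10.2 specifies intention to treat, and nothing says that a missing formal assessment counts as no rapid decline.

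**Conclusion.** The point holds as an inconsistency that should be corrected. The formal week-12 assessment depends on treatment received in one arm, has no latest date, and conflicts with the calendar definition of rapid decline in 2.1 and 7.3. Read literally, it also conflicts with the statements that all participants are assessed at 12 weeks.

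Its size is limited. With cycles in their windows the assessment can be made by day 91 in both arms. Lateness arises only when cycles slip, and where week-24 data exist the composite changes only for participants who recover to within 10%. The net direction is not known, and the protocol does not give the number with delayed or fewer than six cycles. The reason to act is that the week-12 value feeds the primary model and the classification governs counting as not stabilised, rescue and withdrawal. The conclusion rests on reading the six-cycle requirement as written; if sites already use the scheduled week-12 spirometry regardless, the practical effect is smaller still.

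**What to change.** State in 3.4.1 and 7.3 that the rapid-decline component, and the week-12 value in the model of 10.3.1, use the in-clinic spirometry taken at week 12 +/- 7 days in both arms, whatever the number of ECP cycles received. Record the decision on continuing treatment as a separate item with its own date; any six-cycle condition then attaches to that decision and not to the endpoint. Reconcile 5.4.1, 5.4.5, 5.5.1, 5.7 and 7.3, including the maximum gap in 5.7 against the cycle windows in 5.4.1. No dose, schedule or clinical rule needs to be chosen for this purpose.

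The cost is a wording amendment. The week-12 visit already exists, so the only added burden is an occasional second spirometry in the ECP arm when the treatment decision falls later.
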